### 9.8.2 Clinical Laboratory Evaluations

Clinical laboratory evaluations include the continuous variables for hematology, clinical chemistry, and urinalysis. The laboratory values will generally be presented in International System of Units (SI). The on-treatment period will be defined as the time from the first dose of study drug to 100 days after the last dose of study drug. Laboratory values collected during the on-treatment period will be included in the summary tables. The laboratory values collected after the on-treatment period will only be presented in the data listings.

The summary of laboratory data will include shift tables based on CTCAE for shifts in grade from baseline to maximum, minimum and last value during the on-treatment period.

Supporting laboratory data including normal ranges and abnormal laboratory flags will be provided using by-patient listings. Separate listings will be produced for clinically significant laboratory abnormalities (ie, those that meet Grade 3 or Grade 4 criteria according to CTCAE).

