### 3.1.4 Post-treatment Follow-up Phase

All patients will be followed for at least 100 days (+7 days) after the last IV dose of study treatment. The 28-day Follow-up Visit (FU-28) should occur 28 days ( $\pm 3$  days) after last dose of study drug (oral or IV, whichever is later) or can be performed on the date of discontinuation if that date is at least 28 days from the last dose. Assessments will include AEs, physical examination, vital signs and weight measurements, local laboratory hematology, clinical

chemistry, and CA-125 measurement, ECG, ctDNA analysis, concomitant medications, therapies and procedures, and study drug accountability. Follow-up Visit for IV study drug (FU-100) should occur at least 100 days (+7 days) from the last IV dose of study drug. The same assessments performed at FU-28 will be performed at FU-100; however, clinical chemistry and hematology are only necessary if toxicities are present. If a patient remains on oral study drug after discontinuation of IV study drug, FU-100 can be performed at the next cycle visit, provided it has been at least 100 days (+7 days) since the last IV dose.

Patients who discontinue treatment for reason other than disease progression or death should continue to have tumor scans performed at 12-week intervals from Cycle 2 Day 1 (flexibility with scheduling within 1 week prior to planned imaging date is permitted) until objective radiological disease progression by RECIST v1.1 is documented, as assessed by the investigator.

Patients will also be followed long-term for survival, subsequent treatments, disease progression (if treatment discontinuation was for reason other than disease progression or death), and monitoring for secondary malignancy every 12 weeks ( $\pm 14$  days) until death, loss to follow-up, withdrawal of consent, or study closure.

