#### 7.4.7.3 100-day Safety Follow-up (FU-100)

The procedures to be performed for all patients at least 100 days (+7 days) after the last dose of IV study drug are listed below. If a patient remains on oral study drug after discontinuation of IV study drug, the 100-day Safety Follow-up Visit can be performed at a cycle visit, provided it has been at least 100 days since the last IV dose.

- Physical examination
- Weight
- Vital signs
- ECOG performance status ([Appendix 3](#))
- Disease assessment for patients who discontinued treatment for reason other than disease progression or death. Tumor scans should continue to be performed at 12-week ( $\pm 7$  days) intervals for the first 18 months years after initiation of study treatment and every 24 weeks thereafter until radiologic disease progression by RECIST v1.1, as assessed by the investigator, is documented
- Blood sample for ctDNA analysis should be collected at the same time as radiological imaging (Central)
- CA-125 measurement (Local) should be performed at the same time as radiological imaging.

- Hematology (Local) (only required if toxicities are present)
- Clinical chemistry (Local) (fasting is not required) (only required if toxicities are present)
- Urinalysis (Local)
- PK and immunogenicity sample collection (Central) - according to [Table 7](#)
- AE monitoring
- Concomitant medications and procedures

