**Urinalysis:** performed locally on a freshly voided clean sample by dipstick for protein, glucose, blood, pH, and ketones. If dipstick findings are abnormal based on the investigator's judgment, then a microscopic evaluation will be performed to assess the abnormal findings. Urinalysis will be performed at screening, during treatment at each study visit, at the End of Treatment Visit, at the 28-day Follow-up Visit, and at the 100-day Follow-up Visit for all patients, but may be conducted at other times as clinically indicated.

Local laboratory reports will be reviewed by the investigator or delegated physician who will then comment on out of range parameters and assess clinical significance. Clinically significant abnormalities and associated panel results, as well as results of any additional tests performed as follow-up to the abnormalities, will be documented on the eCRF- as an AE. Refer to [Section 8.6](#) for guidelines on reporting of abnormal laboratory values as AEs.

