### 9.8.1 Adverse Events

Adverse events will be classified using the Medical Dictionary for Regulatory Activities (MedDRA) classification system. The severity of the toxicities will be graded according to the NCI CTCAE v5 or later. Only TEAEs will be collected: TEAEs are defined as AEs with onset

date on or after the date of first dose of study drug until 28 days after the last dose of oral study drug or 100 days after the last dose of IV study drug, whichever occurs later.

The number and percentage of patients who experienced TEAEs for each system organ class (SOC) and preferred term will be presented. Multiple instances of the TEAE in each SOC and multiple occurrences of the same preferred term are counted for the worst only once per patient. The number and percentage of patients with at least one TEAE will also be summarized.

Tables for TEAEs and treatment-related TEAEs will be presented as follows but are not limited to:

- All;
- By CTCAE grade;
- Grade 3 or greater;
- Serious;
- TEAEs with an outcome of death;
- TEAEs leading to discontinuation of study drug;
- TEAEs resulting in interruption/delay of study drug; and
- TEAEs resulting in dose reduction of study drug.

The incidence of TEAEs will be summarized by relationship to study drug according to the following categories: “treatment-related,” or “not treatment-related”. If a patient experiences multiple occurrences of the same AE with different relationship categories, the patient will be counted once, as a relationship category of treatment related.

If a patient experiences multiple occurrences of the same AE with different toxicity grades, the patient will be counted once for the maximum (most severe) toxicity grade. AEs with a missing toxicity grade will be presented in the summary table with a toxicity grade of “Missing.” For each toxicity grade, the number and percentage of patients with at least 1 TEAE of the given grade will be summarized.

The time to the first TEAE and first treatment-related TEAE that results in a dose reduction, delay, interruption or discontinuation of study drug is defined as 1+ the number of days from the first dose of study drug to the start of the first adverse event. The cumulative incidence is presented in a 1-KM graph for just the patients with an event and the median time to onset will be calculated together with the 95% CI.

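### Safety summaries are not cut at the start of subsequent anticancer therapy, and the timing of the last laboratory value depends on whether toxicity is present

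*Combined protocol and SAP*

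**What the plan says.** Three safety sections each define a counting period.

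- **Adverse events (9.8.1).** An event is treatment-emergent from the first dose until "28 days after the last dose of oral study drug or 100 days after the last dose of IV study drug, whichever occurs later".
- **Laboratory data (9.8.2).** The rule reads "The on-treatment period will be defined as the time from the first dose of study drug to 100 days" past the final dose. Shift tables compare the baseline grade with the maximum, minimum and last value in that period.
- **Vital signs (9.8.3).** The period is the same as for laboratory data, but only descriptive statistics are planned, not shift tables.

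Sections 9.8.2 and 9.8.3 do not separate oral from IV dosing. Section 3.1.4 times the 28-day visit (FU-28) from the "last dose of study drug (oral or IV, whichever is later", so the later of the two drugs is the natural reading.

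None of the three sections mentions subsequent anticancer therapy. Sections 9.6.2.3 (PFS) and 9.6.2.4 (DOR), by contrast, discard scans taken once another anticancer treatment has begun. Sections 7.4.8 and 7.5.2 collect those treatments for all patients.

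For the 100-day visit (FU-100), Section 3.1.4 says that "clinical chemistry and hematology are only necessary if toxicities are present", and the visit list in Section 7.4.7.3 agrees. The condition goes no further. Vital signs are listed at FU-100 without it, and Section 7.5.4.2 schedules urinalysis "and at the 100-day Follow-up Visit for all patients". At FU-28, hematology and chemistry are unconditional (Section 7.4.7.2).

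**The concern.** A period that stays open for 100 days after the last nivolumab dose is long enough for a patient who has progressed to start another regimen inside it. Section 1.1.1 notes that platinum-sensitive relapse is usually retreated with platinum. Cytopenias or liver-enzyme rises on that regimen would be counted in the same rows as those on rucaparib and nivolumab. These are also the parameters for which Section 9.8.1 builds combined terms (anemia, platelets, neutrophils, ALT/AST). Safety is a secondary objective and both cohorts are small, so a few misplaced events would show.

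The second issue is the shift to the last value. When a late sample is taken only in patients with toxicity, their last value tends to fall near FU-100, while everyone else's falls near FU-28. The column then mixes two follow-up times, and membership of each group depends on the outcome being described.

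**Working it through.** The plan gives no figure to reproduce here. Let O be the last oral day and V the last IV day.

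**1. Counting time after next-line therapy starts.** If both drugs stop on the same day, all the windows close at day 100. If next-line therapy starts s days after the last dose, 100 - s days are still counted. The documents give no s, so 2 to 8 weeks is assumed.

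| s (assumed) | Days still counted | Weeks |
|---|---|---|
| 14 | 100 - 14 = 86 | 12.3 |
| 28 | 100 - 28 = 72 | 10.3 |
| 56 | 100 - 56 = 44 | 6.3 |

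These are days of adverse-event counting. They are not numbers of events or laboratory samples. One affected patient is 1/43 = 2.3 percentage points in a full Cohort A1 and 1/10 = 10 points in Cohort A2.

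**2. Direction for worst grade.** The worst grade over a set of days cannot fall when days are added. Leaving next-line time in therefore leaves worst-grade counts unchanged or raises them.

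**3. Direction for conditional FU-100 sampling.** By the same logic, toxicity-conditional sampling gives a worst-grade rate between that with no day-100 sample and that with full day-100 sampling. The last value is different. As an illustration, assume that 20% of patients have toxicity. Assume the FU-28 value is Grade 3 or higher in 25% of those with toxicity and 2% of those without, and the day-100 value in 15% and 3%.

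- No day-100 sample: 0.2 x 0.25 + 0.8 x 0.02 = 6.6%
- Conditional: 0.2 x 0.15 + 0.8 x 0.02 = 4.6%
- Full: 0.2 x 0.15 + 0.8 x 0.03 = 5.4%

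Here the conditional rule lowers the rate relative to stopping at FU-28. With 40% toxicity and day-100 rates of 30% and 5%, the rate moves the other way. With no day-100 sample it is 0.4 x 0.25 + 0.6 x 0.02 = 11.2%, and with the conditional rule it is 0.4 x 0.30 + 0.6 x 0.02 = 13.2%. The sign depends on whether patients with toxicity recover off drug.

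**4. Difference between the windows.** The laboratory and vital-sign window ends at max(O, V) + 100. The adverse-event window ends at max(O + 28, V + 100), or at O + 28 if nivolumab was never given.

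- O at or before V: both end at V + 100, difference 0.
- O after V: (O + 100) - max(O + 28, V + 100) = min(72, O - V). For O - V = 7, 28 and 72, the difference is 7, 28 and 72 days.
- No nivolumab: (O + 100) - (O + 28) = 72 days.

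The second and third cases can occur. Section 5.5 assesses the two drugs separately, and nivolumab starts only at Cycle 2 Day 1.

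**5. What is scheduled in the difference.** Table 6 lists no hematology or chemistry in long-term follow-up, so after FU-28 the only scheduled draw is FU-100, on V + 100 to V + 107.

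- O - V of 72 or more: V + 100 is no later than O + 28, so FU-100 is already inside the adverse-event window apart from its visit tolerance.
- O - V between 0 and 72: apart from the FU-28 tolerance, the extra days can catch only FU-100 draws on V + 101 to V + 107.
- No nivolumab: there is no IV dose from which to time FU-100, so nothing is scheduled beyond the FU-28 tolerance.

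Otherwise only unscheduled tests can add values.

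**The case against.** The strongest reply is that the long window is deliberate. Immune-mediated events can appear late, and cutting at the next therapy could hide them. Section 9.8.1 also plans separate treatment-related tables, where investigator attribution should remove many next-line events. Section 9.1 leaves further detail to a SAP, and the text supplied holds none beyond protocol Section 9. All of this stands in part. It argues for keeping the uncut tables, but not for having only those. Attribution does not help laboratory shift tables, which carry no causality. The windows themselves are fixed in Section 9.8.

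Some stronger readings are tempting but unsupported.

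- A reader might infer that the shift tables as a whole are biased toward worse values. That holds for worst grade through uncut next-line time. It does not hold for conditional sampling, which gives a worst-grade rate no higher than full sampling and can move the last value either way.
- A reader might infer that about 10 weeks of chemotherapy laboratory data enter the tables. Those weeks are calendar time with very few scheduled draws.
- A reader might treat next-line exposure as a fault of the laboratory window alone. The adverse-event window is equally uncut.
- A reader might extend the sampling argument to vital signs. They have neither the toxicity condition nor shift tables.
- Selective sampling need not arise when rucaparib continues well past nivolumab. FU-100 may then be done at a cycle visit, where hematology and chemistry are drawn anyway.

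**Conclusion.** The point holds as a minor one, in three parts.

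- **No cut at subsequent therapy.** This is the main part and affects adverse events most. For a patient who stops both drugs together, 44 to 86 days of counting would follow a next-line start at 8 to 2 weeks (assumed). The effect on worst-grade counts is zero or upward. Its size cannot be derived from the documents, because it depends on how many patients start another therapy within the window.
- **Last laboratory value.** Its timing depends on toxicity for hematology and chemistry. The direction of bias is undetermined.
- **Window mismatch.** It is at most 72 days, and zero when the last dose is IV. Few draws are scheduled in those days, so the practical effect is small. This part rests on reading the last dose of study drug as the later of oral and IV.

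The primary endpoint is not affected.

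**What to change.** 1. Present the adverse-event and laboratory summaries cut at the start of subsequent anticancer therapy. Keep the uncut versions as supportive, for delayed immune-mediated events. The dates are already collected.
2. Take the hematology and chemistry shift-to-last value from unconditional scheduled visits through FU-28.
3. Use one window definition for adverse events, laboratory data and vital signs, with an allowance that keeps FU-100 visits within the permitted +7 days. Adopting the Section 9.8.1 window unchanged would not do. It drops values on V + 101 to V + 107, which are 7 of the 8 permitted days, unless oral dosing continued to at least V + 73 (for the first of those days) or V + 79 (for the last).

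The cost is a wording change in the analysis plan and a few additional tables. The cut version will also hold fewer late values, which is why the uncut version should stay.

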### 9.8.3 Vital Sign Measurements

The on-treatment period will be defined as the time from the first dose of study drug to 100 days after the last dose of study drug. Vital sign measurements collected during the on-treatment period will be included in the summary tables. The vital sign measurements collected after the on-treatment period will only be presented in the data listings.

The summary of vital sign data will include descriptive statistics (N, mean, StD, minimum, median, third quartile, and maximum) of the maximum, minimum and last value during the on-treatment period. Summaries using descriptive statistics (N, mean, StD, minimum, median and maximum) of the change from baseline to the maximum, minimum, and last value during the on-treatment period will also be given.

## 9.9 Pharmacokinetic Analysis

### 9.9.1 Rucaparib Pharmacokinetic Analysis

In all patients with at least one PK sample collected, the trough plasma rucaparib PK data ( $C_{min}$ ) and summary statistics (N, mean, StD, minimum, median, max, CV%) will be reported.

The PK data may be further analyzed by a PPK approach. The post hoc estimated exposures will be used for ER analyses of selected efficacy and safety endpoints if the data permit. The PPK and the ER analyses may be presented separately from the main clinical study report.

### 9.9.2 Nivolumab Pharmacokinetic Analysis

In all patients with at least one PK sample collected, the serum nivolumab PK data, including  $C_{\min}$  and concentration at the end of infusion ( $C_{\text{eoi}}$ ) and summary statistics (N, mean, StD, minimum, median, max, CV%) will be reported.

The PK data may be further analyzed by a PPK approach. The post hoc estimated exposures will be used for ER analyses of selected efficacy and safety endpoints if the data permit. The PPK and the ER analyses may be presented separately from the main clinical study report.

### 9.9.3 Anti-Nivolumab Antibodies

Anti-nivolumab antibodies in serum samples will be determined. Positive samples will be analyzed for neutralizing antibodies. The results will be reported.

## 9.10 Interim Analysis

An interim analysis of ORR by RECIST v1.1 criteria per investigator for Cohort A1 will be performed at Stage 1 of the Simon 2-stage design for the study. Enrollment in the study will continue while the interim analysis (Stage 1 criteria) occurs for Cohort A1. The DMC will review data for the interim analysis and provide recommendation if Stage 1 criteria are not met for Cohort A1. If Stage 1 criteria are not met, the DMC will evaluate the overall benefit: risk for study treatment, and make a recommendation whether further enrollment should be discontinued. If Stage 1 criteria in the Simon 2-stage design are met, the enrollment will continue with additional patients in Stage 2.

## 10 STUDY ADMINISTRATION

### 10.1 Regulatory and Ethical Considerations

This study will be conducted in compliance with the protocol; Good Clinical Practices (GCPs), including International Council on Harmonization (ICH) Technical Requirements for Registration of Pharmaceuticals for Human Use Guidelines; ICH E6 (R2); FDA regulatory requirements; and in accordance with the ethical principles of the Declaration of Helsinki. The ethical principles underlying European Union Directive 2001/20/EC and the United States Code of Federal Regulations, Title 21, Part 50 and Part 56 (21CFR50), and applicable local requirements.

#### 10.1.1 Regulatory Authority Approvals

The sponsor or designee will submit the study protocol plus all relevant study documents to concerned regulatory agencies for approval prior to the study start. No patient will be admitted to the study until appropriate regulatory approval of the study protocol has been received.

Each investigator must complete a Form FDA 1572 (or equivalent) and provide the completed form according to written instructions to the sponsor (or designee). Each investigator must submit to the sponsor (or designee) financial disclosure information according to national law and/or local regulations.

The study will be registered on [www.clinicaltrials.gov](http://www.clinicaltrials.gov), European Clinical Trials Database (EudraCT), and other applicable trial registry systems as appropriate. Data generated from this study must be handled in accordance with any laws, rules, and regulations related to the privacy of personal data or medical information applicable in the jurisdiction where the data is processed, including without limitation, the United States Health Information Portability and Accountability Act of 1996 (HIPAA), and its implementing regulations, and the European Union General Data Protection Regulation 2016/679 (GDPR).

#### 10.1.2 Institutional Review Board or Independent Ethics Committee Approval

This protocol and any material to be provided to the patient (such as advertisements, patient information sheets, or descriptions of the study used to obtain informed consent) will be submitted by the investigator to an IEC/ IRB. This also applies to protocol amendments.

The sponsor will supply relevant data for the investigator to submit the study protocol and additional study documents to the IEC/ IRB. The principal investigator will submit the study protocol for review and approval by an IEC/ IRB, according to national law and/or local regulations, and will provide the IEC/ IRB with all appropriate materials.

Verification of the IEC's/IRB's unconditional approval of the study protocol and the written ICF will be transmitted to the sponsor. This approval must refer to the study by exact study protocol title and number, identify the documents reviewed, and state the date of the review and approval.

No patient will be admitted to the study until appropriate IEC/ IRB approval of the study protocol has been received, the investigator has obtained the signed and dated ICF, and the sponsor is notified.

The principal investigator will submit appropriate reports on the progress of the study to the IEC/ IRB at least annually in accordance with applicable national law and/ or local regulations and in agreement with the policy established by the IEC/ IRB and sponsor.

The IEC/ IRB must be informed by the principal investigator of all subsequent study protocol amendments and of SAEs or SUSARs occurring during the study that are likely to affect the safety of the patients or the conduct of the study.

## **10.2 Patient Information and Consent**

All information about the clinical study, including the patient information and the ICF, is prepared and used for the protection of the human rights of the patient according to ICH GCP guidelines, applicable regulations, and the Declaration of Helsinki.

It is the responsibility of the investigator to obtain signed ICFs from all patients participating in this study after adequate explanation of the aims, methods, objectives, and potential hazards of the study and prior to undertaking any study-related procedures.

The ICF, prepared by the investigator with the assistance of the sponsor, must be approved along with the study protocol by the IEC/IRB and be acceptable to the sponsor.

The patient must be provided with the patient information and ICF consistent with the study protocol version used and approved by the relevant IEC/IRB. The ICF must be in a language fully comprehensible to the prospective patient. Patients (and/ or relatives, guardians, or legal representatives, if necessary) must be given sufficient time and opportunity to inquire about the details of the study and to discuss and decide on their participation in the study with the investigator concerned. Both the patient and the person explaining the study and with whom the patient can discuss the informed consent will sign and date the ICF. A copy of the signed ICF will be retained by the patient and the original ICF will be filed in the investigator file unless otherwise agreed.

